* Indicates Associate Investigators who will not be involved in clinical decisions or ¹⁸F-DCFBC ordering.

Study Sponsor: National Cancer Institute, Cancer Imaging Program

IND #: 122053

NCI-Supplied Agent(s): ¹⁸F-DCFBC

Other Agent(s): ¹⁸F NaF

Manufacturer: Leidos Biomedical Research, Inc.

CC Protocol Number: 14-C-0140
Abbreviated Title: DCFBC in prostate cancer
Version date: 10/27/2015
CIP #: 9622

Précis

Background

- Prostate cancer is the second leading cause of cancer deaths in American men
- Current methods of imaging advanced prostate cancer (CT and bone scan) are non-specific and new, more specific molecular imaging probes are sought.
- Many prostate cancers express the prostate specific membrane antigen (PSMA) a transmembrane protein with NAALADase enzymatic activity. PSMA is also expressed in angiogenesis but otherwise has limited expression in normal tissue.
- ¹⁸F-DCFBC is a radiolabeled PET agent which binds with high affinity to PSMA and through whole-body non-invasive functional imaging, may provide new information on the expression of PSMA.

Primary Objective

- To assess the ability of ¹⁸F-DCFBC to differentiate between tumorous and non-tumorous tissues in localized, recurrent (based on rising PSA post treatment) and metastatic prostate cancer

Eligibility

- Subject is ≥ 18 years old
- ECOG 0-2 with adenocarcinoma of the prostate and fits criteria for one of the following:
 - ARM 1
 - Patients with known localized prostate cancer with a soft tissue lesion at least 6mm or greater.
 - A multiparametric MRI (standard of care at the NIH Clinical Center) must be performed within 4 months of ¹⁸F-DCFBC injection with findings suggestive for prostate cancer and confirmed with histopathology.
 - ARM 2
 - Patients with biochemical prostate cancer relapse after definitive treatment
 - For patients status post radiation therapy for prostate cancer, any PSA increase from post radiation therapy nadir
 - OR
 - For patients status post prostatectomy, a PSA ≥ 0.2 ng/ml
 - Nonspecific or no evidence for disease on standard imaging modality
 - ARM 3
 - Patients with identifiable metastatic disease on a conventional imaging modality. If only soft tissue metastasis, one lesion must measure 6mm or greater. Patients must have confirmation of prostate cancer prior to ¹⁸F-DCFBC imaging.

[figure not shown]
Design

CC Protocol Number: 14-C-0140
Abbreviated Title: DCFBC in prostate cancer
Version date: 10/27/2015
CIP #: 9622

This is a single site 3-arm study enrolling a total of 110 evaluable patients: Arm 1 will include 12 patients with presumed localized prostate cancer scheduled to undergo prostatectomy or biopsy within 4 months of enrollment; Arm 2 will include 78 patients with biochemical recurrence without evidence of metastasis on conventional imaging; and Arm 3 will include 20 patients with known metastatic disease who may or may not be on or/scheduled to begin therapeutic intervention. Patients with presumed localized disease will undergo a standard of care, clinical multiparametric endorectal coil MRI in the NCI Molecular Imaging Clinic within 4 months of screening. Patients in Arm 3 will undergo 2 imaging sessions: baseline and 4-6 month follow-up. Clinical records (including PSA) and treatment (if any) that occurred in the imaging interval must be available. All patients in Arm 3 will also undergo Na¹⁸F PET/CT for evaluation of bone metastases as part of this protocol. In order to allow for a small number of nonevaluable patients, the accrual ceiling will be set at 125.

CC Protocol Number: 14-C-0140
Abbreviated Title: DCFBC in prostate cancer
Version date: 10/27/2015
CIP #: 9622
Imaging Schema

ARM 1 Suspected localized prostate cancer

[figure not shown]

*Biopsy is standard of care at NCI, prostatectomy will only be performed if clinically indicated and patient wishes to pursue this form of treatment

ARM 2 (biochemical recurrence)

ARM 3 (known metastasis)

Each set of $Na^{18}F$ PET/CT and ^{18}F -DCFBC PET/CT will be done within 3-weeks of each other.

TABLE OF CONTENTS

Summary of Changesiv

Protocol.....iv

Précis.....4

Background4

TABLE OF CONTENTS7

1 Study Objectives10

1.1 Primary Objective.....10

1.2 Secondary Objectives.....10

1.1 Primary Objective

- To assess the ability of ^{18}F -DCFBC to differentiate between tumorous and non-tumorous tissues in localized, recurrent (based on rising PSA post treatment) and metastatic prostate cancer

1.2 Secondary Objectives

- Compare the distribution ^{18}F -DCFBC with multiparametric MRI and whole mount histopathology in patients undergoing prostatectomy
- Evaluate the distribution ^{18}F -DCFBC uptake in prostate cancer patients with biochemical relapse (site of recurrence unknown)
- Compare focal ^{18}F -DCFBC uptake with focal abnormalities identified on standard of care imaging
- Compare the uptake of ^{18}F -DCFBC in bone with respect to Na^{18}F PET/CT in patients with metastatic disease (the emerging gold standard, for detection of bony metastases).
- Evaluate the change over time in ^{18}F -DCFBC distribution in patients with known metastatic disease with clinical follow-up data 4-6 months post baseline ^{18}F -DCFBC PET/CT (e.g. understand the effect of androgen deprivation therapy (ADT) on ^{18}F -DCFBC uptake)

1.3 Exploratory Objective

- If PET/MRI is obtained, findings will be compared with other acquired imaging studies.

2 Background and Rationale

2.1 Prostate Cancer

The lifetime risk of developing prostate cancer for men is 1 in 6. In 2013, it is estimated that 238,590 men will be diagnosed with and 29,720 men will die of cancer of the prostate according to the National Cancer Institute. Many therapeutic options are dependent on the cancer stage at diagnosis and after treatment, recurrent malignancy and accurately defining these stages can be diagnostically challenging. Especially complex is the patient with biochemical recurrence who has no other evidence for cancer except for a suspiciously rising PSA. Accurate assessment at all levels of the disease is critical to guide the best therapy and minimize morbidity related to treatment. Non-invasive methods to detect and monitor this malignancy are limited to PSA for biochemical relapse and CT, US and MRI for standard anatomic morphology. Nuclear medicine has the potential to capture physiologic function but is currently limited to conventional $^{99\text{m}}\text{Tc}$ MDP bone scintigraphy or ^{18}F NaF PET/CT, which is restricted to visualizing bone changes; however the findings can be nonspecific, occur from metastatic disease or benign causes. The only FDA approved molecular imaging radiotracer to detect soft tissue prostate cancer metastasis, ^{111}In Prostascint, has proven to be suboptimal for many reasons and is not routinely used in most clinical settings. Improving molecular imaging capabilities in prostate cancer is crucial to battling this illness.

CC Protocol Number: 14-C-0140
Abbreviated Title: DCFBC in prostate cancer
Version date: 10/27/2015
CIP #: 9622

Much interest has centered on prostate specific membrane antigen (PSMA) as a target for imaging and therapy. Also known as Glutamate Carboxypeptidase II (GCPII) in the central nervous system, PSMA is a type II cell surface membrane glycoprotein receptor found in almost all prostate cancers, especially in advanced, hormone-independent and metastatic disease. It can also be found in the neovasculature of nearly all solid tumors. [1, 2] It is also seen in normal prostate, small bowel, proximal renal tubules, salivary glands and brain but at 100 to 1000 fold lower expression. [3] This normal expression appears to occur within luminal sites which is advantageous in formulating specialized antibodies because they do not need to cross intact basement membranes and tight junctions to bind. Another attractive feature of PSMA is that it does not appear to be secreted in serum, unlike PSA [4]; therefore imaging background due to organ perfusion will be less of an issue. Important to drug development, PSMA bound antibodies undergo internalization through clathrin coated pits. [5] This would give time for targeted imaging once any background activity and non-specific binding clears. These unique characteristics make PSMA a desirable target.

Monoclonal antibodies have been developed against PSMA, but the first agent, ¹¹¹In Prostascint, targets an intracellular epitope that is inaccessible in viable tumor cells which is one factor contributing to its lack of clinical utility.[6] More promising antibodies have been engineered with binding sites to the extracellular domain such as J591 and IgG monoclonal antibodies such as ⁶⁴Cu-3/A12. [7]

J591 is the first humanized monoclonal antibody targeting the extracellular domain of PSMA to be tested in humans. In one trial, 29 patients received ¹¹¹In-J591 for imaging followed by ⁹⁰Y-J591 for therapy. In the parallel trial, 24 patients were treated with ¹⁷⁷Lu-J591, an isotope that can be imaged directly. Overall, of the 43 evaluable patients J591 accurately targeted bone and/or soft tissue lesions in 42 patients (98%). J591 accurately targeted bone lesions in 32 of 34 (94%) and soft tissue lesions in 13 of 18 (72%) evaluable patients. [8] Nargund et al used PSMA scintigraphy with ^{99m}Tc labeled J591 to show usefulness in detecting prostate bed recurrence and distant micrometastasis but not in identifying tumors of the capsule, seminal vesicles or bladder neck.[9] Imaging through PET has been accomplished using ⁶⁴Cu -J591. Evans et al demonstrated that the androgen receptor (AR) is required for androgen repression of PSMA and can be quantitatively imaged with PET. [10] Androgen deprivation therapies, such as MDV3100, increase ⁶⁴Cu -J591 uptake. Illustrating AR signaling changes from pharmacologic intervention in human prostate cancer xenograft models suggests this radiotracer's potential as an imaging biomarker of AR activity.

Disadvantages of radiolabelled antibodies include their large size which slows clearance from the blood pool producing high background radioactivity. The bulky size could also prevent contact with all available binding sites of a heterogeneous tumor. Consequently, binding to target tumor is not quick and can take several days. Small molecule PSMA inhibitors have been created to address this shortcoming. Low-molecular weight compounds have better pharmacokinetics with faster clearance from nontarget tissues and short circulation times in

CC Protocol Number: 14-C-0140
Abbreviated Title: DCFBC in prostate cancer
Version date: 10/27/2015
CIP #: 9622

the blood pool. Typically, these compounds bind to zinc and attach to a glutamate form and belong to 3 different classes- (1) phosphonate-, phosphate-, and phosphoramidate, (2) thiols or (3) ureas.

Urea based scaffolds have yielded the most promising results for molecular imaging. Foss et al first synthesized urea-based small molecule PSMA ligands for PET, ^{11}C -DCMC, and SPECT, ^{125}I -DCIT, and showed specific binding to PSMA in prostate cancer xenograft rodent models.[11] The PET agent has limited clinical use due to the short half-life of 20 minutes for ^{11}C . ^{125}I is produced by nuclear reactor and, with a long half-life (59.4 days) and low energy emissions (27keV) it is suboptimal as an imaging agent. Substitution with ^{123}I (cyclotron produced, primary emission 159keV, half-life of 13.2 days), while imagable with a gamma camera/SPECT, given current limitations SPECT camera yields non-quantitative images with high count loss. ^{68}Ga PSMA ligands to urea compounds have also been produced with good PSMA affinity and tumor-to-background ratios.[12] and can be imaged by PET/CT. A valuable feature of ^{68}Ga -PSMA compounds is that it is a generator produced radiotracer with a reasonable half-life (68 minutes), eliminating the need for a cyclotron and therefore could be more widely available for use.

A significant urea platform for radiolabelling is a lysine glutamate urea molecule and its tri-esters. SPECT agents have been produced from these foundations (^{123}I -MIP-1072 and ^{123}I -MIP-1095), that have good affinity for PSMA and are able to detect metastatic lesions. [13] Structurally similar, Mease et al expanded initial work with carbon-11-labeled compound N-[N-[(S)-1,3-dicarboxypropyl]carbamoyl]-S- ^{11}C methyl-L-cysteine (^{11}C -DCMC) to developing fluorine-18, N-[N-[(S)-1,3-dicarboxypropyl]carbamoyl]-4- ^{18}F fluorobenzyl-L-cysteine (^{18}F -DCFBC) as the first agent designed specifically for clinical PET imaging of prostate cancer.[14]

2.2 ^{18}F DCFBC (CIP # 122053)

^{18}F DCFBC is a small molecule targeting an external binding domain of PSMA. Mease et al described the synthesis, in vivo behavior and human dosimetry estimates using mouse biodistribution data for ^{18}F DCFBC.[14] Mice were implanted with PSMA+ and PSMA – prostate cancer cell lines and injected with ^{18}F DCFBC. PSMA has N-acetylaspartyl-glutamate (NAAG) peptidase activity which was utilized to determine ^{18}F DCFBC's inhibitory capacity for PSMA through the NAAG peptidase inhibition assay. Findings of 13.9 nmol/L for IC50 value were consistent with other compounds of this class. At 60 minutes after radiotracer injection, rodents had the highest uptake in the kidneys and urinary bladder as well as in the PSMA+ tumor. Little to no uptake was noted in PSMA- cells. Physiologic

CC Protocol Number: 14-C-0140
Abbreviated Title: DCFBC in prostate cancer
Version date: 10/27/2015
CIP #: 9622

excretion occurred through the kidneys and bladder and by 2 hours, renal radioactivity was confined to the cortex. Target to muscle background ratio of 10:1 at 60 min and 20:1 was seen at 120 min after injection. Clearance from non-target tissue was faster than from target sites. Low uptake in normal bone was noted indicating no significant defluorination of ^{18}F DCFBC, which will allow visualization of bone metastasis.

Their human dosimetry estimates based on the animal model [14] calculate the highest absorbed dose to the kidneys at 0.0487 mGy/MBq (0.2 rad/mCi). The mean absorbed dose to the liver was 0.009 mGy/MBq and .0005 mGy/MBq to the brain. The effective dose equivalent was .005 mSv/MBq and the effective dose was .003 mSv/MBq. Administering a dose of 185 to 370 MBq (5-10 mCi) ^{18}F DCFBC yields acceptable absorbed dose estimates for nuclear medicine diagnostic procedures.

Cho et al followed up with initial clinical experience with ^{18}F DCFBC in metastatic prostate cancer patients.[15] Five patients with metastatic disease were injected with 370 MBq (10 mCi) of ^{18}F DCFBC and serial PET/CTs obtained for 2 hours after injection. Based on visual and quantitative assessment, the highest ratio of tumor activity to background was seen at the 2 hour scan. PET images were considered positive if focal radioactivity was above adjacent background tissue or blood pool for lymph nodes or bone. Lean body mass maximum standardized uptake values (SUV_{max}) were obtained for regions-of-interest (ROIs) for quantitative measurements. Focal abnormal PET uptake was seen in 32 metastatic lymph nodes and bone lesions with median SUV_{max} of 5.6 for lymph nodes, and 3.6 for bone. Conventional imaging was concordant with PET findings in 21 sites, 5 of them bone. Discordant positive PET findings were attributed to possible early bone metastases or subcentimeter lymph nodes. All 10 positive sites on conventional imaging that were negative on PET, were in bone and considered indeterminate for malignancy or due to trauma. One true metastatic bone lesion that was PET negative could have been related to antiandrogen therapy.

Metabolite analysis was also done in 2 patients with high performance liquid chromatography with essentially no metabolism or defluorination of ^{18}F DCFBC in plasma at approximately 1 and 2 hours after injection. Radioactivity remained almost entirely within the blood plasma.

Surprisingly, blood pool activity remained moderately persistent through imaging. Possible explanations include binding to a free form of PSMA circulating in the blood. They tested the inhibitory capacity of unlabeled DCFBC to prevent PSMA from hydrolyzing N-acetylated aspartyl-glutamate in normal human plasma and found 3nM was the 50% inhibitory concentration.

Dosimetry calculations showed a mean effective dose of 19.9 ± 1.34 uSv/MBq. The highest mean absorbed dose (uGy/MBq) was the urinary bladder wall (32.4) then the stomach wall

CC Protocol Number: 14-C-0140
 Abbreviated Title: DCFBC in prostate cancer
 Version date: 10/27/2015
 CIP #: 9622

(30.2), heart wall (29.2) and kidneys (28.4). Similar to preclinical findings, ^{18}F DCFBC, cleared through urinary excretion with PSMA-mediated uptake in normal renal tissue. No significant brain uptake was noted consistent with the radiotracer's hydrophilic nature (and resultant inability to cross the blood-brain barrier). Effective dose estimates are comparable to ^{18}F FDG (used in clinic routinely) which is 1.90×10^{-2} mSv/MBq and ^{18}F DCFBC averages 1.99×10^{-2} mSv/MBq per administered dose. Their dosimetry calculations are below.

Organ	Average
Adrenals	1.85E-02
Brain	4.21E-03
Breasts	8.51E-03
Gallbladder wall	1.79E-02
Lower large intestine wall	2.47E-02
Small intestine wall	2.36E-02
Stomach wall	3.02E-02
Upper large intestine wall	2.34E-02
Heart wall	2.92E-02
Kidneys	2.84E-02
Liver	2.46E-02
Lungs	2.45E-02
Muscle	9.69E-03
Ovaries	1.32E-02
Pancreas	1.92E-02
Red marrow	1.70E-02
Osteogenic cells	1.82E-02
Skin	7.30E-03
Spleen	1.72E-02
Testes	1.54E-02
Thymus	1.10E-02
Thyroid	1.17E-02
Bladder wall	3.24E-02
Uterus	1.34E-02
Total body	1.09E-02
Effective dose	1.99E-02

Figure 1: Average Organ-Absorbed Dose (mGy/MBq) and Estimated Effective Dose (mSv/MBq) [15]

In this study, none of the 5 patients experienced any severe adverse events. There were 3 minor adverse events that were classified as either unrelated or unlikely to be attributable to the radiopharmaceutical. Two patients experienced grade 3 blood pressure events using the Common Terminology Criteria for Adverse Events (National Cancer Institute) on routine vital sign assessment after administration of the radiopharmaceutical (patient 1 unrelated; patient 2 unlikely), both of which resolved on 7-d follow-up assessment. Several days after administration of the radiopharmaceutical, a third patient experienced lower back pain that began during physical exertion and was considered unrelated to the radiopharmaceutical.

[figure not shown]

Figure 2 ^{18}F -DCFBC PET anterior projection maximal-intensity-projection images at 2 h after injection in patient 1, with several bone metastases (arrow) (A), and patient 5, with LN metastases (arrow) (B), as confirmed by correlation to CT portion of PET/CT exam. [15]

2.2.1 Toxicity and Pharmacology

2.2.1.1 Toxicity in animals

A toxicity report “Single Dose Toxicity Study of ^{19}F -DCFBC (NSC-743104) in Rats” was prepared by Bridge GPS, Inc. (Study No. 1535-07015). The following summary is taken from that report.

This study was designed to determine target organ toxicity of ^{19}F -DCFBC (NSC-743104) and its reversibility in rats treated with a single intravenous dose.

Sixty Fischer 344 rats (30/sex) were randomly assigned to one of three dose groups (10/sex/group) based on body weight and physical examination. Five rats/sex/group were designated to the main phase of the study, and five rats/sex/group were designated to the recovery phase of the study. All animals were dosed once on Study Day (SD) 1 via intravenous injection (tail vein) with either the control article (5% dextrose) or ^{19}F -DCFBC (NSC-743104) at nominal dose levels of 0.1 or 0.5 mg/kg. Terminal sacrifice necropsies were performed on SD 4; recovery sacrifice necropsies were performed on SD 15. Parameters evaluated during the study included mortality, clinical and cage side observations, body weights, body weight changes, clinical pathology parameters (clinical chemistry and hematology), gross pathology and histopathology. Mortality, clinical and cage-side observation, body weight and body weight changes, clinical pathology, gross pathology and histopathology were unaffected by treatment.

Based on the results of this study, a single intravenous injection of ^{18}F -DCFBC (NSC-743104) at doses up to 0.5 mg/kg to male and female Fischer 344 rats was well tolerated.

CC Protocol Number: 14-C-0140
Abbreviated Title: DCFBC in prostate cancer
Version date: 10/27/2015
CIP #: 9622
2.2.1.2 Toxicity in Humans

Cho et al [15] studied five patients with metastatic prostate cancer and none experienced any severe adverse events. There were 3 adverse events that were classified as either unrelated or unlikely to be attributable to the radiopharmaceutical. Two patients experienced grade 3 blood pressure events using the Common Terminology Criteria for Adverse Events (National Cancer Institute) on routine vital sign assessment after administration of the radiopharmaceutical (patient 1 unrelated; patient 2 unlikely), both of which resolved on 7-d follow-up assessment. Several days after administration of the radiopharmaceutical, a third patient experienced lower back pain that began during physical exertion and was considered unrelated to the radiopharmaceutical.

2.2.2 Safety

Cho et al [15] demonstrated that radiation doses to patients with ^{18}F DCFBC are comparable to other PET radiopharmaceuticals such as ^{18}F FDG with the overall effective dose for ^{18}F -DCFBC averaging 1.99×10^{-2} mSv/MBq per administered dose (vs. ^{18}F -FDG, estimated at 1.90×10^{-2} mSv/MBq).

2.2.3 Catheter Placement

DCFBC is physiologically excreted through the bladder making visualization of surrounding tissue, (primarily the prostate bed in our situation) extremely challenging. In Arm 2 patients specifically, we are looking for possible recurrence within the region that may be very small and often overshadowed by the adjacent high urine activity. Mertens et al., described using a catheter during FDG imaging that significantly improved visualization and quantification of primary bladder cancer [17]. Other groups have also shown better evaluation of gynecologic tumors using catheter irrigation [18]. We are hoping to similarly optimize our ability to accurately find disease by reducing bladder activity with the catheter.

2.3 Rationale

We propose to further expand upon initial clinical work with ^{18}F DCFBC and evaluate its usefulness in three different categories of prostate cancer- localized, metastatic and biochemical recurrence. In the case of localized disease ^{18}F DCFBC distribution will be compared with endorectal coil multiparametric MRI at 3T. In the case of potentially recurrent or metastatic disease ^{18}F DCFBC will be compared with CT, bone scan and/or Sodium Fluoride PET/CT bone scan. This study should offer insights into how and when ^{18}F DCFBC could be used in the clinical setting to direct proper management. Moreover, by monitoring ^{18}F DCFBC uptake in metastatic disease over time, one may better understand how useful this agent may be in monitoring responses to therapy.

Amendment C Addendum:

The agent has shown some preliminary promising results. In Arm 2, we have had patients with questionable uptake only near the bladder. We have noted that bladder activity may obscure possible prostate bed recurrence, so a recent amendment was approved for urinary catheterization with possible bladder irrigation. We have only been able to scan a limited

CC Protocol Number: 14-C-0140
Abbreviated Title: DCFBC in prostate cancer
Version date: 10/27/2015
CIP #: 9622

number of patients using this technique and have been able to locate areas suspicious for recurrence in some. Additional patients will help to determine if the technique is beneficial in visualization, potentially improving detection rates for early local recurrence. In Arm 3, we have noted a mixed response in tracer uptake for hormone sensitive patients, which contradicts what other PSMA research groups are reporting. They assert that uptake is always positive in patients on anti-androgen treatment. Our findings could be due to the heterogeneous evolution of lesions to castrate resistance, but currently our numbers are small. More patients to this arm will allow better characterization of the relationship between 18F DCFBC uptake and androgen deprivation therapy.

Amendment E Addendum:

To date 31 patients have been scanned on Arm 2. All are assumed to have recurrent disease based on rising PSA. There have been 20 positive scans (9 in the prostate bed, 8 outside the prostate bed (nodes or bone) and 3 both in and out of the prostate bed. Biopsy is only available in 7 but clinical information is supportive (i.e. response to therapy) in 4 more. Thus, the results are still preliminary. In the range of PSA 0.2-0.5ng/ml the scan is 25% positive, 0.5-1.0 ng/ml 50% 1.0 to 2.0ng/ml 40% and >2.0ng/ml 85%. However, the first 10 patients were done without irrigation catheters and this undoubtedly explains some of the findings. The first expansion request for Arm 2 was to get more patients with bladder irrigation catheters after we recognized that bladder-urethra activity was probably hiding some lesions. We now have over 20 patients in that category. Having shown some promising results, the purpose of this expansion cohort is to better define the sensitivity of DCFBC as a function of serum PSA. This should be a useful metric for comparing DCFBC with the next agent, DCFPyl which is reputed to have higher sensitivity. Thus, the basis of our request is to obtain more accurate assessment of the sensitivity of this agent as a function of PSA in patients with biochemical recurrence.

CC Protocol Number: 14-C-0140
Abbreviated Title: DCFBC in prostate cancer
Version date: 10/27/2015
CIP #: 9622

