4.8 Biopsy

Biopsy of abnormal sites of uptake will not be required by this protocol; however if a suspicious focus of uptake is identified, this information will be communicated to the referring physician, who may choose to evaluate the site further with biopsy or clinical follow-up. In such a case any follow-up information obtained (including pathology) will be collected as clinically needed.

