14 STATISTICAL CONSIDERATIONS

14.1 Primary Analysis

This is a single site three-arm pilot study, where prostate cancer patients are enrolled into different arms according to their disease types: localized (Arm 1), recurrent (Arm 2) or metastatic (Arm 3). The primary objective of this study is to assess the ability of ^{18}F -DCFBC to identify sites of localized, recurrent and metastatic prostate cancer. To achieve this goal, ^{18}F -DCFBC PET/CT and conventional imaging will be used to identify positive suspected sites, and the proportion of positive concordance will be used to assess the performance of ^{18}F -DCFBC. In a recent study (Cho et al., 2012), 32 positive suspected sites in five prostate cancer patients with metastasis were identified by ^{18}F -DCFBC PET/CT with 21 concordant on both ^{18}F -DCFBC PET/CT and conventional imaging. At the individual level, the number of positive suspected sites ranged from 2 to 12 with the patient-specific concordance rate ranging from 0 to 100%. The overall concordance rate which was the average of individual-specific estimates across patients equaled 64% with corresponding standard deviation equal to 43%. For the new study, assume that for patients in Arm 1 and Arm 3, the mean concordance rate is 70% with 43% standard deviation as observed in Cho et al. With 12 evaluable patients in Arm 1, the 90% expected confidence interval for the mean concordance rate is (0.50, 0.90). With 20 evaluable patients in Arm 3, the 90% expected confidence interval for the mean concordance rate is (0.54, 0.86). For patients in Arm 2 (recurrent disease), it is unlikely to identify suspected lesions by conventional imaging at the baseline. These patients will be followed according to the protocol.

Amendment E Addendum:

Sensitivity of ^{18}F -DCFBC uptake in prostate cancer patients in Arm 2 is evaluated by its ability in differentiating mean values of PSA between PET-CT positive and PET-CT negative patients. To this end, the current study with sample size 35 for Arm 2 is under-powered to detect a sizeable mean difference in PSA between the two groups. Based on the preliminary data of the study, log-transformed PSA is approximately normally distributed with standard deviation equal to 1.3. Assume 1:2 allocation of PET-CT negative vs. PET-CT positive

CC Protocol Number: 14-C-0140
Abbreviated Title: DCFBC in prostate cancer
Version date: 10/27/2015
CIP #: 9622

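### Arm 2 *sensitivity by PSA* has no rule for a true-positive scan, so the plan yields a positivity rate and a PSA association, not sensitivity

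*Combined protocol and SAP*

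**What the plan says.** All references are to the combined protocol and SAP.

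- **Purpose.** Section 2.3, Amendment E Addendum: "the purpose of this expansion cohort is to better define the sensitivity of DCFBC as a function of serum PSA". The same paragraph offers the result as a yardstick for comparison with the next agent.
- **Reference standard.** Same paragraph: "All are assumed to have recurrent disease based on rising PSA".
- **Interim data.** "To date 31 patients have been scanned on Arm 2", followed by "There have been 20 positive scans (9 in the prostate bed, 8 outside the prostate bed (nodes or bone) and 3 both in and out", the last group being positive at both sites. By rising PSA band, 25%, 50%, 40% and 85% of scans are described as positive.
- **Verification so far.** "Biopsy is only available in 7 but clinical information is supportive (i.e. response to therapy) in 4 more". The results are called preliminary.
- **Analysis.** Section 14.1, Amendment E Addendum, says that Arm 2 sensitivity "is evaluated by its ability in differentiating mean values of PSA between PET-CT positive and PET-CT negative patients". The 78 evaluable patients (26 negative, 52 positive) are sized for a two-sided Wilcoxon test on that difference.
- **Verification planned.** Section 4.8: "Biopsy of abnormal sites of uptake will not be required by this protocol". Section 4.1 plans biopsy validation of Arm 2 uptake where it is possible, and collects clinical, imaging and pathology data for 12 months to look for associations. Sections 4.10 and 12.1.1 provide for one year of follow-up data.

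**The concern.** Sensitivity needs a disease status, and a definition of a correct positive, that do not depend on the scan. Here disease status is assigned to every man from his PSA, and a positive scan is accepted as it stands. Under that convention no positive call can be wrong. A focus that is not tumor still counts as a success, because the man is assumed to have disease somewhere.

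Section 14.1 does not repair this. A difference in PSA between scan-positive and scan-negative men says that positivity tracks PSA. It does not say what fraction of diseased men are detected, and it also takes each scan result at face value.

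The later use of the figure is what is at stake. A tracer with more non-specific uptake would score higher on a positivity rate that is called sensitivity, so a comparison with the next agent on that figure could favour the less specific tracer.

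**Working it through.** **1. The plan's own figure.** Inputs from section 14.1: log-PSA means 0.06 and 0.98, SD 1.3, two-sided 5% Wilcoxon test, 26 negative and 52 positive.
- Effect: 0.98 − 0.06 = 0.92, and exp(0.92) = 2.51, which matches the stated 2.5-fold ratio.
- Monte Carlo power (20,000 samples): 80.8% at 26:52, against 80% stated; 46.5% at 12:23 (35 patients), against 48% stated.

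The sample size reproduces. It is the size for a PSA comparison. Section 14.1 gives no target precision for a proportion in Arm 2.

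**2. What the assumption does to the formula.** Sensitivity = true positives ÷ diseased. With all scanned men set to diseased and all positives taken as true, this becomes positives ÷ scanned, the positivity rate.

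The effect of false calls, with assumed rates: if true detection is s and a fraction g of the remaining men get a false-positive call, expected positivity is s + (1 − s)g.
- s = 50%, g = 10%: 0.50 + 0.50 × 0.10 = 55%.
- s = 50%, g = 30%: 0.50 + 0.50 × 0.30 = 65%.

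The figure rises while true detection stays at 50%. The rates are illustrative; the documents give none.

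**3. Interim counts (section 2.3), exact Clopper-Pearson 90% intervals.**
- Positive scans: 9 + 8 + 3 = 20. 20/31 = 64.5% (48-79%).
- Any stated support: 7 biopsied + 4 clinical = 11 at most. 11/31 = 35.5% (21-52%).
- Positives with no stated support: at least 20 − 11 = 9, which is 9/20 = 45% of positives.

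Eleven is a ceiling. Section 2.3 does not give the seven biopsy results or say that all seven were in scan-positive men. If no biopsy confirmed cancer, support would fall to 4/31 = 13%. Patient numbers per PSA band are not given, so these checks cannot be repeated by band.

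**4. Search for a truth rule elsewhere.** Section 4.8 does not require biopsy. Section 4.1 has biopsy where possible, plus follow-up for associations. Section 14.2 plans patient-specific sensitivity and specificity only for localized disease. No section says how biopsy, imaging or treatment response would reclassify a positive Arm 2 scan.

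**The case against.** The strongest reply is that nothing has been misreported. Section 2.3 labels its interim percentages as positive scans, says that disease is assumed, discloses how few biopsies exist and calls the results preliminary. This stands. The problem is the stated purpose of the expansion and the wording of section 14.1, not a mislabelled interim result.

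The protocol also provides for some verification through biopsy where possible and a year of follow-up. This stands too, and it makes the remedy cheap. What is missing is a classification rule and a table.

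Three stronger readings are tempting, and the documents do not support them:
- *The gap between 65% and 35% is bias.* The gap is 9/31 = 29 points of unverified status. Unverified does not mean false, and no false-positive Arm 2 scan is documented.
- *65% and 35% bound sensitivity.* The lower figure assumes seven confirming biopsies that are not reported. The upper figure is a ceiling only if all 31 men have recurrence, yet section 3.1 admits men after radiation on any PSA rise from nadir. As an illustration, if 5 of the 11 scan-negative men had no recurrence and all 20 positives were true, sensitivity would be 20/26 = 77%.
- *Doubtful uptake beside the bladder inflated the count.* The Amendment C Addendum mentions such uptake but does not say that those scans were called positive. The protocol's main worry is the reverse, that bladder activity hides lesions, and it introduced catheters for that reason.

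Finally, this protocol contains no formal comparison with the next agent. Any harm comes later, from how the figure is used.

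**Conclusion.** The concern holds in this limited form. A stated assumption (all men diseased) and a stated analysis (PSA by scan result) do not produce the stated quantity (sensitivity by PSA). Followed as written, the plan gives a positivity rate and a PSA association.

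On the interim data, positivity is 65% (90% CI 48-79%), support is present in at most 35% of men (21-52%), and at least 9 of 20 positives have no stated support. These figures keep all 31 men in the denominator as diseased and give every biopsy the benefit of the doubt. They measure how much is unverified. They do not estimate the size or the direction of the error in sensitivity, because men without recurrence among the scan-negatives would push the other way. The power calculation is sound for the test that it describes.

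**What to change.** In sections 2.3 and 14.1:
1. Keep the Wilcoxon test and its sample size, but describe the test as the association of PSA with scan positivity.
2. Add the detection (positivity) rate by PSA band, with exact intervals, as the quantity that the expansion estimates. Do not call it sensitivity.
3. Pre-specify a composite confirmation rule from the biopsy, imaging and treatment-response data already collected within 12 months. In each band, report the confirmed-positive rate beside positivity, with confirmed, refuted and unverified positives shown separately.
4. Do not present the two rates as bounds on sensitivity unless the text says that this holds only if all men have recurrence.

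The cost is revised wording, one extra table and a less favourable label. No new biopsies, scans or patients are needed.
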